8.1.2 Medical management

ACEs and ARBs are considered as SoC therapy in patients with DKD and often prescribed to patients with DKD at early stages (8).

It is advisable to follow the recommendations of local guidelines for the management of CVD and CKD, the use of statins, anti-platelets and beta-blockers, and for glycemic control.

8.1.3 Control of blood pressure - amended

This section was changed in Amendment 3, see Section 15.1.2.10.

According to international guidelines, the recommended target blood pressure for subjects with T2DM and albuminuria, who are at increased risk of CVD and CKD progression, is <130/80 mmHg (39-41). However, this value may vary for the individual subject depending on concomitant diseases and well-being.

If blood pressure is considered uncontrolled by the investigator during the study period, non-potassium-sparing diuretics may be added as first choice to the treatment regimen if this was not already done. Thereafter, the addition of antihypertensive medication can be performed according to local guideline recommendations.

All concomitant medication added to the treatment regimen during the course of the study must be recorded in the eCRF.

8.1.4 Use of potassium supplements and lowering agents

If needed, potassium supplementation can be prescribed during the course of the study. Investigators are advised to monitor potassium carefully at each visit and to adapt the dose of any potassium supplementation in accordance with the potassium value measured at each visit or discontinue potassium supplementation once the potassium is within the normal range.

Potassium-lowering agents (e.g. sodium polystyrene sulfonate, calcium polystyrene sulfonate) are allowed to be started during treatment with study drug.

Any use of potassium supplementation and potassium-lowering agents must be documented in the eCRF.

8.2 Post-study therapy

The investigator will decide in consultation with the individual subject if additional treatment is required and choose from existing treatment options.

The investigator must provide follow-up medical care for all subjects who complete the study or who are prematurely withdrawn from the study, or must refer them for appropriate ongoing care as required.

9. Procedures and variables

9.1 Tabular schedule of evaluations - *amended*

This section was changed in Amendment 3, see Section 15.1.2.11 and Section 15.1.2.12.

Table 9–1 depicts the schedule of activities and evaluations for this study (16244).

An overview of the procedures for sub-studies of 16244 is provided in Table 9–2.

All randomized subjects will remain in the study until its termination, either:

- (1) after positive adjudication of the targeted number of primary efficacy endpoint events,
or
- (2) at a recommendation of the DMC.

Thus, all subjects, including those who stopped taking study drug, should be asked to attend all the protocol-specified study visits in order to perform all assessments as stipulated in the visit schedule (Table 9–1).

If any subject refuses to return for the defined assessments or is unable to do so, every effort should be made to contact him/her or a knowledgeable informant by telephone to ask if any of the primary, secondary, or other endpoints have been reached at the scheduled visits for the remaining duration of the study (see Section 6.4.1.1 for details). Attempts to contact the subject should be documented in the subject's records. If any subject refuses to be contacted by telephone (e.g. the subject withdrew consent to release further information), every effort should be made to obtain vital status (alive or dead) information through consultation of public databases, wherever allowed by local regulations.

Table 9–1 Study 16244: schedule of activities and evaluations - amended

Visit	Run-in	Screening	Visit 1 (Baseline)	Visit 2	Visit 3	Visit 4, 6, 7, 9, etc ^h	Visit 5, 8, 11, etc	Up-titration Visit ^j	PD Visit	EOS Visit ^k	PT Visit ^m
Day / Month	4 to 16 weeks pre-screening	≤ 2 weeks	Day 1	Month 1	Month 4	(every 4 months, i.e. Month 8, 16, 20, 28, etc)	(every 12 months, i.e. Month 12, 24, 36, etc)	For up-titration/restart after interruption, and for safety check 4 weeks ± 7 days after any up-titration (see also footnote j)	As soon as possible but within 7 days after SD is permanently discontinued	After study termination	4 weeks + 5 days after last SD intake
Informed consent	X										
In- and exclusion criteria	X	X	X								
Demographic data	X										
Smoking status	X										
Alcohol consumption	X										
Medical history	X										
Prior medication	X										
Concomitant medication	X	X	X	X	X	X	X	X	X	X	X
Randomization			X								
Drug accountability				X	X	X	X	X	X	X	
Study drug dispense			X	X	X	X	X				
Study drug administration			X		X						
KDQOL-36, EQ-5D-5L			X				X		X	X	
Physical examination	X	X					X		X	X	
Weight, height, waist and hip circumference ^a	X	X	X	X	X	X	X	X	X	X	
Vital signs ^b	X	X	X	X	X	X	X	X	X	X	
12-lead ECG (local)	X	X	X				X		X	X	
PK blood sample					X ⁿ		X ^o				
Full central laboratory	X	X	X		X	X	X		X	X	
Limited chemistry (central)				X				X			
Urinalysis (central) ^c	X	X	X		X		X			X	
Safety laboratory (local) ^d			X	X	X	X	X	X			
Endpoint assessment ^e				X	X	X	X	X	X	X	
AE assessment ^f	X	X	X	X	X	X	X	X	X	X	X
Pregnancy test ^g		X					X				

Table 9–1 Study 16244: schedule of activities and evaluations - amended**NOTE:**

One month corresponds to 30 days

A time frame of ± 7 days is allowed for Visit 2 (Month 1), and for the Up-titration Visit(s).

A time frame of ± 12 days is allowed for all regular visits from Visit 3 (Month 4) onwards.

Abbreviations: ECG = electrocardiogram; EOS = end of study; EQ-5D-5L = EuroQol Group 5 dimension, 5 level questionnaire; KDQOL = Kidney Disease Quality of Life; PD = premature discontinuation; PT = post-treatment; (S)AE = (serious) adverse event; SD = study drug

- ^a Height, waist and hip circumference to be assessed at Run-in Visit only.
- ^b After resting for at least 5 minutes, 3 measurements to be taken with at least 1-minute interval in a sitting position (all 3 readings within a maximum of 20 minutes).
- ^c At Visit 1, first morning void urine samples to be preferably collected on three consecutive days at the subject's home within 7 days before scheduled visit and before any intake of study drug. At the other visits the 3 consecutive samples can be collected ± 7 days from the visit date.
- ^d Blood samples (for potassium and creatinine) for measurement in the local laboratory may be obtained up to 72 hours before a scheduled visit. Samples to be taken only if the subject is still taking study drug,
- ^e Categorical renal endpoints, $\geq 40\%$ or $\geq 57\%$ decrease in eGFR compared to baseline and an eGFR decrease to less than 15 mL/min/1.73 m², have to be confirmed by at least one additional standardized serum creatinine measurement. This confirmation should be done at least 4 weeks after the initial measurement as an unscheduled assessment.
- ^f AEs related to study procedures occurring after signing the informed consent as well as all other AEs starting after randomization will be documented on the respective eCRF pages.
- ^g Female subjects of childbearing potential must have a negative serum or urine pregnancy test at screening and yearly thereafter (to be performed at the local laboratory). If required by national / institutional regulations, a serum or urine pregnancy test in subjects of childbearing potential should be performed more often (e.g. at every visit, see Section 9.7.2).
- ^h Every 4 months until study termination, excluding the yearly visits (i.e. Visits 5, 8, 11, etc., at Months 12, 24, 36, etc.).
- ^j The "Up-titration Visit" should be performed for up-titration (at any time after Visit 2), after restart of SD after an interruption for >7 days, and for safety check 4 weeks ± 7 days after any up-titration.
- ^k After the study site is notified about study termination, an EOS Visit must be performed for all the subjects as soon as possible and within 4 weeks at the latest.
- ^m For all the subjects still on treatment with study drug at the EOS Visit, the PT Visit has to be performed 4 weeks + 5 days after last intake of study drug and will be performed by a telephone contact (except for subjects participating in the iohexol sub-study).
- ⁿ A trough PK sample will be drawn before study drug is administered at the study center by study personnel. The exact time of study drug intake on the day before the visit and on the day of the visit and the exact sampling time will have to be recorded in the eCRF. If the trough sample was not taken at Visit 3 it should be obtained at Visit 4 (see Section 9.5).
- ^o Study drug will be taken as usual, ideally in the morning at home. One PK sample will be drawn during the visit. The exact time of study drug intake and the exact sampling times will have to be recorded in the eCRF.

Table 9–2 Sub-studies of Study 16244: schedule of procedures – amended

Visit	Run-in	Screening	Visit 1 (Baseline)	Visit 2	Visit 3	Visit 4, 6, 7, 9, etc	Visit 5, 8, 11, etc	Up-titration Visit	PD Visit	EOS Visit	PT Visit ^c
Day / Month	4 to 16 weeks pre-screening	≤ 2 weeks	Day 1	Month 1	Month 4	(every 4 months, i.e. Month 8, 16, 20, 28, etc)	(every 12 months, i.e. Month 12, 24, 36, etc)	For up-titration/ restart after interruption, and for safety check 4 weeks ± 7 days after any up-titration	As soon as possible but within 7 days after SD is permanently discontinued	After study termination	4 weeks + 5 days after last SD intake
Informed consent ^a			X								
Echocardiography ^f			X				X		X ^e	X ^e	
Sampling for biomarkers			X		X		X		X ^e	X ^e	
Iohexol clearance ^b			X		X	X ^d	X ^d		X ^e	X ^e	X

NOTE:

One month corresponds to 30 days.

A time frame of ± 7 days is allowed for Visit 2 (Month 1).

A time frame of ± 12 days is allowed all regular visits from Visit 3 (Month 4) onwards.

Abbreviations: EOS = end of study; PD = premature discontinuation PK = Pharmacokinetics; PT = post-treatment; SD = study drug

^a Separate informed consent for each sub-study is required.

^b Sites in Italy only.

^c For all the subjects still on treatment with study drug at the EOS Visit, the PT Visit has to be performed 4 weeks + 5 days after last intake of study drug.

^d Every other visit (every 8 months) , i.e. Visit 5, Visit 7, Visit 9, Visit 11, etc.

^e Assessment at the end of the study, either at the PD Visit or the EOS Visit.

^f Time window for the assessment at Visit 1 is -14/+7 days, at other visits +/-30 days. Each time an echocardiography is performed, one blood sample should be drawn to assess the echo biomarkers

9.2 Visit description - amended

This section was changed in Amendment 3, see Section 15.1.2.13.

One month in the study schedule corresponds to 30 days. Although study visits should occur as close as possible to the time points specified in the protocol, a time frame of ± 7 days is allowed for Visit 2 (Month 1), and for the Up-titration Visit(s). Starting from Visit 3 (Month 4), a time frame of ± 12 days is allowed for all regular visits.

All procedures and assessments should preferably be conducted on the day of the visit; however, if this is not possible for logistical reasons, the following time windows are allowed:

Blood sampling, ECG and recording of vital signs:

- Screening Visit and all the visits starting from Visit 2: Visit date ± 7 days
- Run-In, PD and EOS Visit: Visit date ± 3 days

Sub-studies / iohexol and biomarker samples:

- all visits starting from Visit 3: Visit date ± 7 days
- PD and EOS Visit: Visit date ± 3 days

Sub-study / echocardiography (note that each time an echocardiography is performed, one blood sample should be drawn to assess the echo biomarkers):

- at Visit 1: Visit date -14 / +7 days
- Other visits: Visit date ± 30 days

NOTE: If applicable, a subject who is not eligible at the Run-in or Screening Visit may be re-screened at a later time (see Section 6.4.2.1) or switch over to Study 17530 (see Section 6.4.2.2) provided the pre-requisites are met.

9.2.1 Run-in Visit (4 to 16 weeks prior to the Screening Visit) - amended

This section was changed in Amendment 3, see Section 15.1.2.14.

The following procedures and assessments will be performed at the Run-in Visit:

- Obtain signed informed consent (may be done earlier).
NOTE: any study-specific procedure can be performed only if written informed consent is **available**
- Check inclusion and exclusion criteria (see Sections 6.1 and 6.2)
- Collect demographic data, smoking status and alcohol consumption (see Section 9.3.1)
- Record medical history (see Section 9.3.2)
- Record use of prior and concomitant medication (see Section 8.1)
- Perform physical examination (see Section 9.7.3)
- Record body weight, height, waist and hip circumference (see Section 9.7.4)

- Record vital signs (see Section 9.7.5)
- Perform 12-lead ECG (see Section 9.7.6)
- Take samples (hematology, HbA_{1c}, chemistry and urinalysis) for central laboratory evaluations (see Section 9.7.2.1).
Note: If HbA_{1c} cannot be analyzed by the central laboratory due to technical reasons, subject can be considered suitable for randomization with one result only (Run-In or Screening).
- Record adverse events (see Section 9.6.1), accounting for the rules of assessment and documentation (see Section 9.6.1.3)

9.2.2 Screening Visit (≤ 2 weeks prior to Visit 1) - *amended*

This section was changed in Amendment 3, see Section 15.1.2.15.

The following procedures and assessments will be performed at the Screening Visit:

- Check inclusion and exclusion criteria (see Sections 6.1 and 6.2)
- Record use of concomitant medication (see Section 8.1)
- Perform physical examination (see Section 9.7.3)
- Record body weight (see Section 9.7.4)
- Record vital signs (see Section 9.7.5)
- Perform 12-lead ECG (see Section 9.7.6)
- Take samples (hematology, HbA_{1c}, chemistry, urinalysis) for central laboratory evaluations (see Section 9.7.2.1)
Note: If HbA_{1c} cannot be analyzed by the central laboratory due to technical reasons, subject can be considered suitable for randomization with one result only (Run-In or Screening).
- Record adverse events (see Section 9.6.1), accounting for the rules of assessment and documentation (see Section 9.6.1.3)
- Perform pregnancy test (see Section 9.6.2).

9.2.3 Visit 1 (randomization; Day 1 and baseline) - *amended*

This section was changed in Amendment 3, see Section 15.1.2.16.

All measurements on Visit 1 are to be performed on the day of the visit before first study drug intake. The following procedures and assessments will be performed at Visit 1:

- Instruct the subject on how to complete KDQOL-36 and EQ-5D-5L questionnaires; the subject completes the questionnaires (see Section 9.7.7).
- Obtain informed consent for sub-studies (see Section 9.7.8.1)
- Check inclusion and exclusion criteria (see Sections 6.1 and 6.2)

- Record use of concomitant medication (see Section 8.1)
- Record body weight (see Section 9.7.4)
- Record vital signs (see Section 9.7.5)
- Perform 12-lead ECG (see Section 9.7.6)
- Take samples (hematology, HbA_{1c}, chemistry, urinalysis) for central laboratory evaluations (see Section 9.7.2.1)
- Take samples (potassium, creatinine) for local safety laboratory evaluations (see Section 9.7.2.2)
- Optional: if the subject had signed informed consent for the sub-study, obtain respective samples for biomarkers (see Section 9.7.8.1.2) and/or iohexol clearance (see Section 9.7.8.1.3), perform echocardiography (see Section 9.7.8.1.1)
Note: Time window for the echocardiography at Visit 1 is -14/+7 days. On the day the echocardiography is performed, a blood sample should also be drawn to assess the echo biomarkers.
- Randomization to finerenone or placebo once daily (see Section 7.1)
- Dispense the study drug (see Section 7.2)
- Record adverse events (see Section 9.6.1), accounting for the rules of assessment and documentation (see Section 9.6.1.3)
- First administration of study drug.

9.2.4 Visit 2 (Month 1)

The following procedures and assessments will be performed at Visit 2:

- Record use of concomitant medication (see Section 8.1)
- Collect unused study drug and perform accountability to assess compliance (see Section 7.6)
- Dispense the study drug (see Section 7.2)
- Record body weight (see Section 9.7.4)
- Record vital signs (see Section 9.7.5)
- Take samples (limited chemistry) central laboratory evaluations (see Section 9.7.2.1)
- Take samples (potassium, creatinine) for local safety laboratory evaluations (see Section 9.7.2.2)
- Assess if the subject has any endpoint event(s) (see Table 13–1 and Section 9.6.1.3.1)
- Record adverse events (see Section 9.6.1), accounting for the rules of assessment and documentation (see Section 9.6.1.3).

9.2.5 Visit 3 (Month 4) - amended

This section was changed in Amendment 3, see Section 15.1.2.17.

Ideally, the study personnel should contact the subject prior to Visit 3 to remind them not to take the study drug as usual in the morning at home. The following procedures and assessments will be performed at Visit 3:

- Record use of concomitant medication (see Section 8.1)
- Collect unused study drug and perform accountability to assess compliance (see Section 7.6)
- Dispense the study drug (see Section 7.2)
- Record body weight (see Section 9.7.4)
- Record vital signs (see Section 9.7.5)
- Take samples (hematology, HbA1c, chemistry, urinalysis) for central laboratory evaluations (see Section 9.7.2.1)
- Take samples (potassium, creatinine) for local safety laboratory evaluations (see Section 9.7.2.2)
- Obtain pre-dose sample for PK (see Section 9.5)
- Administer study drug after PK sample has been obtained (see Section 9.5)
- Optional: if the subject had signed informed consent for the sub-study, obtain respective samples for biomarkers (see Section 9.7.8.1.2) and/or iohexol clearance (see Section 9.7.8.1.3)
- Assess if the subject has any endpoint event(s) (see Table 13–1 and Section 9.6.1.3.1)
- Record adverse events (see Section 9.6.1), accounting for the rules of assessment and documentation (see Section 9.6.1.3).

9.2.6 Visit 4, 6, 7, 9, etc. (every 4 months; Month 8, 16, 20, 28, etc., excluding yearly visits) - amended

This section was changed in Amendment 3, see Section 15.1.2.18.

The following procedures and assessments will be performed at Visit 4, 6, 7, 9, etc.:

- Record use of concomitant medication (see Section 8.1)
- Collect unused study drug and perform accountability to assess compliance (see Section 7.6)
- Dispense the study drug (see Section 7.2)
- Record body weight (see Section 9.7.4)
- Record vital signs (see Section 9.7.5)

- Take samples (hematology, HbA_{1c}, chemistry) for central laboratory evaluations (see Section 9.7.2.1)
- Take samples (potassium, creatinine) for local safety laboratory evaluations (see Section 9.7.2.2)
- **Visit 4 only:** Obtain pre-dose sample for PK if no PK sample was taken at Visit 3 (see Section 9.5)
- Optional: if the subject had signed informed consent for the sub-study, obtain samples for iohexol clearance (see Section 9.7.8.1.3)
Note: Iohexol clearance should be performed every 8 months only (Visit 7, Visit 9, etc.)

- Take samples (potassium, creatinine) for local safety laboratory evaluations (see Section 9.7.2.2)
- Assess if the subject has any endpoint event(s) (see Table 13–1 and Section 9.6.1.3.1)
- Record adverse events (see Section 9.6.1), accounting for the rules of assessment and documentation (see Section 9.6.1.3).

9.2.9 Premature Discontinuation (PD) Visit (as soon as possible but within 7 days after study drug is permanently discontinued) - amended

The section title was changed in Amendment 3, see Section 15.1.2.21.

If the PD visit cannot be performed within the timeframe specified, no PD visit is required. The following procedures and assessments will be performed at the PD Visit:

- The subject completes KDQOL-36 and EQ-5D-5L questionnaires (see Section 9.7.7)
- Record use of concomitant medication (see Section 8.1)
- Collect unused study drug and perform accountability to assess compliance (see Section 7.6)

- Perform physical examination (see Section 9.7.3)
- Record body weight (see Section 9.7.4)
- Record vital signs (see Section 9.7.5)
- Perform 12-lead ECG (see Section 9.7.6)
- Take samples (hematology, HbA_{1c}, chemistry) for central laboratory evaluations (see Section 9.7.2.1)
- Optional: if the subject had signed informed consent for the sub-study, obtain respective samples for biomarkers (see Section 9.7.8.1.2) and/or for iohexol clearance (see Section 9.7.8.1.3), perform echocardiography (see Section 9.7.8.1.1)
- Assess if the subject has any endpoint event(s) (see Table 13–1 and Section 9.6.1.3.1)
- Record adverse events (see Section 9.6.1), accounting for the rules of assessment and documentation (see Section 9.6.1.3).

9.2.10 End of study (EOS) visit - *amended*

This section was changed in Amendment 3, see Section 15.1.2.22.

The following procedures and assessments will be performed at the EOS Visit:

- The subject completes KDQOL-36 and EQ-5D-5L questionnaires (see Section 9.7.7)
- Record use of concomitant medication (see Section 8.1)
- Collect unused study drug and perform accountability to assess compliance (see Section 7.6)
- Perform physical examination (see Section 9.7.3)
- Record body weight (see Section 9.7.4)
- Record vital signs (see Section 9.7.5)
- Perform 12-lead ECG (see Section 9.7.6)
- Take samples (hematology, HbA_{1c}, chemistry, urinalysis) for central laboratory evaluations (see Section 9.7.2.1)
- Optional: if the subject had signed informed consent for the sub-study, obtain respective samples for biomarkers (see Section 9.7.8.1.2) and/or for iohexol clearance (see Section 9.7.8.1.3), perform echocardiography (see Section 9.7.8.1.1)
- Assess if the subject has any endpoint event(s) (see Table 13–1 and Section 9.6.1.3.1)
 - Any eGFR declines that meet endpoint criteria that are identified at the EOS Visit, or that cannot be confirmed by the time of the EOS Visit, should be confirmed 4 weeks after the initial decline

- In exceptional circumstances only, if the subject is unable to attend this visit during the given timeframe, the subject (or primary physician/ next of kin) should be contacted to obtain survival status.
- Record adverse events (see Section 9.6.1), accounting for the rules of assessment and documentation (see Section 9.6.1.3).

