Discontinuation of study drug (for any reason) does not constitute the subject's withdrawal from the study, except if the investigator believes that it is in the best interest of the subject or if the subject withdraws consent (see Section 6.4.1 for details).

Details on procedures that are important to ensure the safety of the individual study subject are provided in the relevant sections of this protocol (i.e. *medical management, control of blood pressure and use of potassium supplements/lowering agents* in Section 8.1, and *monitoring blood potassium* in Section 9.7.1).

Follow-up Period

The period between the subject's last intake of study drug and last visit in the study is referred to as the '*Follow-up Period*'. If a subject withdraws from study drug permanently but does not withdraw from the study, this would apply to the period between the Premature Discontinuation (PD) Visit, which should take place as soon as possible following permanent discontinuation of study drug, and the EOS Visit. In the case where a subject discontinues treatment at the EOS Visit, the Follow-up Period applies to the period between the EOS visit and PT visit.

All subjects who had withdrawn consent can be followed up for vital status if they do not sign the '*Declaration of Objection*' form. In addition, vital status can be obtained by the investigator from publicly available data sources. The collection of vital status must be obtained within the timelines provided by Bayer.

End of study

The end of the study as a whole will be reached as soon as the last visit of the last subject of Study 16244 has been reached in all centers in all participating countries (EU and non-EU).

The study will terminate either when:

- (1) the targeted number of primary efficacy endpoint events have been positively adjudicated
- OR
- (2) at a recommendation of the DMC, whichever is earlier.

After notification of study termination, for all subjects still participating in the study, an End-of-Study (EOS) Visit should be scheduled as soon as possible (within 4 weeks of notification at the latest) to determine whether the subject had an event for inclusion in the primary or secondary endpoints.

Subjects who are still on treatment will discontinue study drug treatment at the EOS Visit and must perform the Post-Treatment (PT) Visit (4 weeks + 5 days) after their last dose of study drug.

The primary completion event for this study is the last visit for the last subject.

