6.4 Withdrawal of subjects from study

6.4.1 Withdrawal

6.4.1.1 Discontinuation of study drug - *amended*

This section was changed in Amendment 3, see Section 15.1.2.6.

After randomization, discontinuation of **study drug** (for any reason) does not constitute the subject's withdrawal from the **study** (see also Section 6.4.1.2).

Study drug *must* be permanently discontinued if any of the following occurs:

- Pregnancy of the study subject (see also Section 9.6.2)
- The investigator is of the opinion that continuation of treatment with study drug is harmful to the subject's well-being
- The randomization code is broken by the investigator, or other responsible person, when knowledge of the subject's treatment is required
- Any investigational drug other than the study drug is used.

Study drug *may* be permanently discontinued if any of the following occurs:

- Any suspected drug-related AE or SAE
- If any exclusion criterion applies during treatment
- If a significant violation of the protocol occurs, as defined by the sponsor and the coordinating investigator.

In general, subjects who permanently discontinue study drug are expected to continue in the follow-up period and to attend all protocol-specified study visits, and should be encouraged to perform all assessments described in the visit schedule (see Section 9.2).

If a subject no longer on study drug is unable to attend the clinic for a study visit, a telephone consultation may be performed to determine if relevant health events /endpoints (e.g. development of CV or renal complications) have occurred. Ideally, a face-to-face visit should be performed at least once a year. Expected frequency of telephone contacts should be in line with the standard visit schedule, and therefore performed every 4 months. Ad hoc additional telephone contacts may also be requested (e.g. prior to the interim analysis) and made to the subject themselves or to other contact as provided by the patient, e.g. a next of kin, primary physician (or local equivalent).

Note that study drug may be temporarily discontinued (i.e. interrupted), as described in Section 7.4.

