6.2.2 Analysis of secondary efficacy variables

6.2.2.1 Secondary efficacy variables: primary analysis

Secondary efficacy variables are as follows:

- Time to first occurrence of the following CV composite endpoint: cardiovascular (CV) death or non-fatal CV events (i.e. myocardial infarction, stroke, or hospitalization for HF)
- Time to all-cause mortality

- Time to all-cause hospitalization
- Change in UACR from baseline to Month 4
- Time to first occurrence of the following renal composite endpoint: onset of kidney failure, a sustained decrease in eGFR of $\geq 57\%$ from baseline over at least 4 weeks or renal death.

The primary analysis of the secondary efficacy variables will be conducted in the FAS.

See section 4.7 for the testing hierarchy for secondary endpoints and for multiplicity adjustment of significance levels.

The primary analysis of the secondary time-to-event endpoints will be conducted analogously to the primary analysis of the primary composite endpoint, with modifications to the censoring rules as the events will differ. In the event of premature termination from the study with no subsequent follow-up information, subjects without any information about the composite endpoint after baseline will be censored at Day 1, and the following censoring rules will also apply:

- CV events will be counted up to the day of withdrawal from the study or non-CV death. Randomized subjects without an event of the CV composite endpoint at the time of analysis will be censored at the date of their last contact up to and including the EOS visit or date of non-CV death.
- Hospitalization events will be counted up to the day of withdrawal from the study or death. Randomized subjects without a hospitalization event at the time of analysis will be censored at the date of their last contact up to and including the EOS visit or date of death.
- All-cause mortality will be counted up to the last date vital status could be obtained. Randomized subjects without such an event at the time of analysis will be censored at the last date vital status could be obtained up to and including the EOS visit.

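### When the End-of-Study visit cannot be attended, Protocol 9.2.10 asks only for survival status, which conflicts with 9.1; the SAP's undefined last contact may then count that call as event-free CV and hospitalization follow-up

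*Protocol*

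**What the plan says.** Protocol Section 5 (End of study) gives the purpose of the EOS visit: "to determine whether the subject had an event for inclusion in the primary or secondary endpoints". It is to take place within 4 weeks of notification that the study is ending.

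Protocol 9.2.10 lists endpoint assessment among the EOS procedures. Under it is a fallback, added by Amendment 3: "In exceptional circumstances only, if the subject is unable to attend this visit during the given timeframe", then "the subject (or primary physician/ next of kin) should be contacted to obtain survival status".

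Protocol 9.1 has a general rule for non-attenders. It opens "If any subject refuses to return for the defined assessments or is unable to do so" and requires every effort to reach the subject or an informant "by telephone to ask if any of the primary, secondary, or other endpoints have been reached at the scheduled visits for the remaining duration". Vital status alone is the last resort, for those who also refuse telephone contact. For subjects off study drug, Protocol 6.4.1.1 adds that "a telephone consultation may be performed to determine if relevant health events /endpoints" have occurred, and 11.4 allows physicians, relatives and records as sources.

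SAP 6.2.2.1 states that subjects without a CV composite event "will be censored at the date of their last contact up to and including the EOS visit or date of non-CV death". The hospitalization rule is parallel, with death in place of non-CV death. All-cause mortality has its own rule, based on the last date at which vital status was known. SAP 6.2.1.1 censors the renal composite at the last visit with complete information on every component.

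**The concern.** Three texts govern the last point at which events can be found, and they do not agree. Section 9.2.10 applies the weakest form of follow-up (alive or dead) to someone who can be reached by telephone. Section 9.1 reserves that form for people who refuse to be telephoned. A site working from the EOS procedure list could follow 9.2.10 alone and not ask about dialysis, transplant, myocardial infarction, stroke or hospitalization since the last regular visit.

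The SAP has no safeguard against this for two endpoints. If a survival-only call counts as the last contact, the subject gains event-free time that nobody verified. One of the two, the CV composite, is the key secondary endpoint and carries its own share of alpha (SAP 4.7). Subjects who cannot travel to a final visit may be sicker than average, so the missing information could be related to the outcome.

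**Working it through.** **1. What the follow-up rules require**

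| Protocol text | Who | What is asked |
|---|---|---|
| 9.1, general rule | Anyone refusing or unable to return | Primary, secondary and other endpoints, by telephone |
| 9.1, last resort | Those who also refuse calls | Vital status |
| 6.4.1.1 and 11.4 | Subjects off study drug | Health events and endpoints, by telephone or from other sources |
| 9.2.10 | Subjects unable to attend EOS in time, exceptionally | Survival status |

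A subject still on drug who cannot attend EOS falls under both 9.1 (endpoint enquiry) and 9.2.10 (survival only). Neither section refers to the other on this point.

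**2. What each SAP censoring rule requires**

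- Renal composite (6.2.1.1): complete component information. A survival-only call cannot move the censoring date. Where no EOS visit took place, events still count up to notification + 4 weeks, so capturing a late dialysis or transplant start depends on the 9.1 enquiry or another source.
- CV composite and hospitalization (6.2.2.1): last contact, undefined, with no condition on what was asked.
- All-cause mortality (6.2.2.1): last date of known vital status. A survival-only call is sufficient here.

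**3. Would the sensitivity analysis show it?** SAP 6.2.2.2 extends the tipping-point analysis to the key secondary endpoint. Appendix A imputes for subjects lost to follow-up or with consent withdrawn, from last contact to notification + 4 weeks. If a survival call near that cut-off is the last contact, almost no time is left to impute.

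**4. Size (illustration)**

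The plan gives no figure to reproduce here: no non-attendance share, CV rate or hospitalization rate.

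Inputs from the documents: N ≈ 5800 (SAP Section 3); visits every 4 months (Protocol Section 5) with a window of ±12 days and 30-day months (Protocol 9.2).

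Assumed: gap since the last endpoint enquiry = 4 months + 12 days = 4.4 months = 0.367 years; share with a survival-only contact 0.5–5%; CV rate 3–8% per year; hospitalization rate 30% per year.

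Unseen events = N × share × (1 − exp(−rate × gap)). For example, 5800 × 0.05 × (1 − exp(−0.08 × 0.367)) = 290 × 0.0289 = 8.4.

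| Share | Subjects | Patient-years | CV, 3%/y | CV, 8%/y | Hospitalization, 30%/y |
|---|---|---|---|---|---|
| 0.5% | 29 | 10.6 | 0.3 | 0.8 | 3.0 |
| 1% | 58 | 21.3 | 0.6 | 1.7 | 6.0 |
| 5% | 290 | 106.3 | 3.2 | 8.4 | 30.2 |

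All counts are across both arms. They are high in two respects: they assume that no other source reports the event, and that every affected subject was event-free before the gap. They are low if non-attenders have above-average rates, since the counts grow roughly in proportion to the rate. With the longest gap, (120 + 12 + 28)/30 = 5.3 months, the 5% row rises to at most 10.1 CV events and 36.0 hospitalizations.

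Power for the CV composite, by Schoenfeld's formula Φ(√D × |ln HR|/2 − z), assuming D = 800 events and HR 0.80: losing 10 events costs 0.6 percentage points at the 0.01576 level and 0.4 at the 0.04967 level.

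**The case against.** A reader might infer that sites are told to ask about nothing but survival, that the SAP counts the call as event-free follow-up, and that the last months' events are therefore lost. The documents do not support that chain.

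- The fallback is limited to exceptional circumstances. It sets what must be obtained and does not forbid further questions. Section 9.1 still applies to anyone unable to return, and endpoint assessment and adverse event recording stand beside the fallback in the same EOS list.
- The SAP does not say that a survival-only call is a last contact. Its separate vital-status date for mortality allows the opposite reading, that vital-status enquiries are distinct from contacts.
- SAP 6.2.1.1 provides for a missing EOS visit by counting renal events to notification + 4 weeks, so it expects event information from other routes.
- Every rate behind the event counts is assumed, and a 5% share fits poorly with exceptional circumstances. The documents give no reason for non-attendance to differ by arm in a double-blind trial.

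All of this stands, and it limits the point to a conflict between two protocol sections and an undefined SAP term. It does not remove either. The more specific text asks for less than the general one, and the condition that protects the renal censoring date is absent for the CV composite and hospitalization.

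**Conclusion.** The inconsistency is real: 9.2.10 conflicts with 9.1 and with the stated purpose of the EOS visit. Because last contact is undefined in SAP 6.2.2.1, a survival-only call may add unverified event-free time for the CV composite and all-cause hospitalization. The documents do not show that it will, or that events will in fact be lost. The primary endpoint's censoring date is not affected; only the capture of late dialysis or transplant starts depends on the 9.1 enquiry.

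The likely effect is small: about 0.3–8 CV events and 3–30 hospitalizations across both arms under the assumptions above, with a minor effect on power. Bias by arm is possible but not indicated by anything in the plan. The case for changing the text is that the repair is cheap and both endpoints are in the formal testing sequence.

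**What to change.** 1. **Protocol 9.2.10.** Have the fallback contact carry out the 9.1 endpoint enquiry together with survival status: dialysis, kidney transplant, myocardial infarction, stroke and any hospitalization since the last visit. Keep survival status alone for subjects who refuse the enquiry.
2. **SAP 6.2.2.1.** Censor the CV composite and all-cause hospitalization at the last contact at which that endpoint status was obtained. Use vital-status-only contacts for all-cause mortality alone.
3. **Reporting.** Give the number of survival-only EOS contacts by arm.

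The cost is a few more questions in a call that is already required, one censoring sentence and one table row. The downside is slightly less person-time for subjects whose final contact gave vital status only.
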